6.4 Handling of Drug Data

Subsequent treatment will be classified based on the Prescription Drug Data File, Version 2020.10 or later. Classification by "types of subsequent treatment" is as specified in the attachment.

7 STATISTICAL ANALYSIS AND SUMMARY

7.1 Primary Endpoint

7.1.1 Overall survival (OS)

The data will be summarized using the Kaplan-Meier method and plotted on graphs. OS will be estimated for median and 95%CI.

7.1.2 Sensitivity analysis/supportive analysis for the primary endpoint

Not applicable

7.2 Secondary Endpoints

Percentage of subjects receiving subsequent treatment

The number and percentage of subjects will be calculated for treatment lines (First, Second) and types of subsequent treatment. Changes in subsequent treatment in subjects who proceeded to receive subsequent treatment will be summarized and plotted on graphs.

Subsequent-treatment period

Data for each treatment line will be summarized using a Kaplan-Meier method and plotted on graphs. The duration of subsequent-treatment period for each treatment line will be estimated for median and 95%CI. The same analyses will be performed for each type of subsequent treatment per treatment line.

The duration of all subsequent treatment will be plotted for each subject.

7.3 Other Endpoints

Clinical Efficacy of Subsequent Treatment

- Compute the percentage of subjects applicable to each category of clinical efficacy by each type of subsequent treatment.
- Compute the percentage of subjects applicable to each category of clinical efficacy by each treatment line.

The clinical efficacy of each and every subsequent treatment will be plotted for each subject along with the duration of the subsequent treatment.

Time to start of chemotherapy

The data will be summarized using the Kaplan-Meier method and plotted on graphs. The median time to start of chemotherapy and its 95%CI will be estimated.

Dose Adjustment of Palbociclib

- Compute the percentage of subjects applicable to each type of dose reduction.
- Compute the percentage of subjects applicable to each reason for dose reduction.

Duration of Treatment with Palbociclib + Letrozole

The duration of treatment with palbociclib + letrozole will be plotted for each subject. For palbociclib, the duration of treatment will be plotted by dose groups.

7.4 Subgroup Analyses

The same analysis described in "7.1 Primary Endpoint" will be performed for each category shown in "4.4 Major Baseline Variables" and for each category of the duration of palbociclib treatment (threshold: median, 24 months).

The following subgroup analyses will be performed based on the Kaplan-Meier method used for the Subsequent-treatment period (First Line) specified in 7.2 "Secondary Endpoints."

- Types of First Line
- Disease Site (visceral, non-visceral)

Plots for each subject in the subsequent-treatment period as per 7.2 "Secondary Endpoints" will be used to perform the following subgroup analyses.

- Disease Free Interval since completion of prior therapy
- Disease Site (visceral, non-visceral)
- Duration of treatment with palbociclib (threshold, median, 24 months)

The following subgroup analyses will be performed based on the Kaplan-Meier analyses for time to start of chemotherapy specified in 7.3 "Other Endpoints."

- Disease Free Interval since completion of prior therapy

- Disease Site (visceral, non-visceral)

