9.3. Variables

The same patient IDs will be used for this study and J-Ph2. Data collected in this study will be combined and evaluated with J-Ph2 data, including patient demographics, study treatment, and baseline tumor assessment, through matching with patient IDs. Variables and data sources are described in Table 1. Detailed definitions will be included in the statistical analysis plan (SAP).

Table 1. Variables in this study

Variable	Role	Data source(s)
Overall Survival	Outcome	J-Ph2 database A5481154 database
Type of subsequent therapy	Outcome	J-Ph2 database A5481154 database
Duration of subsequent therapy	Outcome	J-Ph2 database A5481154 database
Clinical response of subsequent therapy	Outcome	A5481154 database
Palbociclib dose modification	Exposure, Outcome	J-Ph2 database A5481154 database
Palbociclib treatment duration	Exposure, Outcome	J-Ph2 database A5481154 database
Letrozole treatment duration	Exposure, Outcome	J-Ph2 database A5481154 database
Demographic and baseline characteristics	Baseline characteristics	J-Ph2 database

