3 STUDY DESIGN

This is a Japanese, multicenter, retrospective, observation study. This observation study is designed as a follow-up study to the Japanese phase 2 study of palbociclib (NCT01684215, the phase 2 part of Study A5481010; hereinafter, J-Ph2). In J-Ph2, 43 subjects were enrolled and 42 received palbociclib plus letrozole. Eight deaths were reported at the end of J-Ph2 (i.e., last subject last visit [LSLV], October 25, 2018). Of the remaining 34 subjects with no reported deaths, 4 refused further follow-up and 30 were being followed up for survival.

Medical charts of those 30 subjects in the post-J-Ph2 survival period will be used to retrospectively collect OS and subsequent-treatment data. For subjects transferred to another hospital, the investigator will be requested to make his/her utmost efforts to collect data from the hospitals to which the subjects were transferred. The investigator will complete paper-based case report forms (CRFs) at the start of the study at each site and during the annual reporting period specified by the sponsor. Subject IDs assigned in J-Ph2 will be used to collate the subject demographics and other relevant data between this observation study and J-Ph2 and to analyze the data.

Eight subjects with OS events confirmed in J-Ph2 and 4 who refused to continue follow-up after J-Ph2 will be analyzed based on data collected in J-Ph2.

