4 DEFINITIONS OF ENDPOINTS AND BASELINE VARIABLES

4.1 Primary Endpoint

Overall survival (OS)

Defined as time from the date of the first dose of the investigational product in J-Ph2 to the date of any-cause death. Subjects whose death was unconfirmed will be censored at the last date of confirmed survival.

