4.3 Other Endpoints

Clinical efficacy of subsequent treatment (categories: complete response, partial response, stable disease, progression, unknown)

- Percentage of subjects applicable to each category of clinical efficacy by each type of subsequent treatment
- Percentage of subjects applicable to each category of clinical efficacy by each treatment line

Time to start of chemotherapy

Defined as time from the date of the first dose of the investigational product in J-Ph2 to the date of the first subsequent chemotherapy or any-cause death, whichever occurred first. Surviving subjects who had not started subsequent chemotherapy will be censored at the last date of confirmed survival.

Dose Adjustment of Palbociclib

- Percentage of subjects by types of dose reduction (category: no dose reduction, dose reduction by 1 level to 100 mg, dose reduction by 2 levels to 75 mg, others)
- Percentage of subjects by reasons for dose reduction (category: adverse event, others) among those who reduced doses

Duration of Treatment with Palbociclib + Letrozole

The duration of treatment with palbociclib per dose (category: 125 mg, 100 mg, 75 mg, etc.) is defined as time from the date of the first dose to the end of treatment with the dose level.

The duration of treatment with letrozole is defined as time from the date of the first dose per investigational product in J-Ph2 to the date of the last dose of letrozole.

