4.4 Key Baseline Variables

J-Ph2 database will be used for the following classification.

- ECOG PS
- Disease Free Interval since completion of prior therapy
- Prior Adjuvant Anticancer Treatment
- Disease Site (visceral, non-visceral)
- Disease Site (bone only, other)
- Age (<65, >=65)
- Dose Reduction Group
- Prior Chemotherapy
- Prior Endocrine Therapy
- Ki67 Status (<=20%, >20%)

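### SAP 7.4 compares OS from first dose between groups formed by later palbociclib duration and dose reduction, so immortal time favours longer-treated and dose-reduced patients

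*SAP*

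**What the plan says.** SAP 4.1 starts the OS clock at first dose: "Defined as time from the date of the first dose of the investigational product in J-Ph2 to the date of any-cause death". SAP 7.1.1 summarises OS by Kaplan-Meier: "OS will be estimated for median and 95%CI".

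SAP 7.4 repeats that analysis within each category of the SAP 4.4 variables and also "for each category of the duration of palbociclib treatment (threshold: median, 24 months".

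The SAP 4.4 list of key baseline variables includes "Dose Reduction Group", with no definition or time window. Its only indication of source is that "J-Ph2 database will be used for the following classification". SAP 4.3 uses dose reduction as an on-treatment outcome ("Percentage of subjects by types of dose reduction"). Protocol Table 1 (9.3) gives "Palbociclib dose modification" and palbociclib treatment duration the role of exposure and outcome, drawn from both databases, and lists baseline characteristics separately.

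SAP 7.1.2 plans no sensitivity or supportive analysis of OS. Protocol 9.9 names the single arm, the difficulty of causal attribution and the small sample, but not this problem.

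**The concern.** A Kaplan-Meier comparison from time zero requires groups that are known at time zero. Treatment duration is not. Membership of the 24-months-or-more group guarantees survival to month 24, so that curve is flat at 100% until then. A patient who dies on treatment at month 10 is placed in the short group because she died. The split at median duration works the same way.

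Reading the dose reduction group as SAP 4.3 uses the term (an inference, since 4.4 does not define it), a patient must survive and remain on palbociclib long enough to be reduced. Early deaths therefore collect in the unreduced group.

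At stake is interpretation. Published OS medians with confidence intervals by treatment duration or dose reduction could be read as evidence that longer treatment, or reduction, goes with longer survival, when part or all of the difference comes from how the groups were formed.

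**Working it through.** The plan gives no figure for these subgroups to reproduce, so the check asks how large a difference appears when duration and dose reduction have no effect on survival.

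**Inputs from the documents.** 42 treated patients; "Eight deaths were reported at the end of J-Ph2" (SAP 3), with no split by month 24; 1-year PFS 75.0%, 90% CI 61.3% to 84.4% (Protocol 7).

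**Assumptions.** PFS stands in for time on palbociclib, which is not reported. OS is Weibull, S(t) = exp{-ln2 (t/m)^k}, with k = 1.5 or 2 and median m = 60, 72 or 84 months. Stopping is exponential with rate λ and independent of death. Duration = min(stopping, death). Follow-up is complete.

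**Step 1, early deaths.** Expected deaths before month 24 = 42 × (1 − S(24)).

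**Step 2, group medians at cut c.** Let p = exp(−cλ). The long group (stopping and death both after c) has its median where S(t) = ½S(c). The short group has its median where S(t) = ½{1 − pS(c)}/(1 − p). Invert with t = m(−ln s/ln2)^(1/k).

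**Step 3, calibration.** A: min(stopping, death) is 75% at month 12, so 12λ = −ln 0.75 − ln2 (12/m)^k. B: stopping alone is 75% at month 12, so p at month 24 is 0.75² = 0.5625.

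**Worked case** (k = 1.5, m = 60, A, c = 24). S(24) = 0.839; 12λ = 0.2877 − 0.0620 = 0.2257; p = exp(−0.4514) = 0.637. Long: S(t) = 0.420, t = 69.7 months. Short: S(t) = 0.641, t = 44.6 months. Gap 25.1 months.

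| k | m | Deaths before month 24 | 24-month cut, A: long vs short (gap) | 24-month gap, B | Median-split gap, A | Median-split gap, B |
|---|---|---|---|---|---|---|
| 1.5 | 60 | 6.8 | 69.7 vs 44.6 (25.1) | 21.1 | 26.6 | 20.1 |
| 1.5 | 72 | 5.2 | 81.0 vs 58.6 (22.4) | 19.7 | 24.1 | 19.4 |
| 1.5 | 84 | 4.2 | 92.3 vs 71.9 (20.4) | 18.5 | 22.2 | 18.7 |
| 2 | 60 | 4.4 | 64.6 vs 53.4 (11.2) | 10.4 | 12.3 | 10.5 |
| 2 | 72 | 3.1 | 75.9 vs 66.6 (9.2) | 8.8 | 10.5 | 9.4 |
| 2 | 84 | 2.3 | 87.4 vs 79.5 (7.9) | 7.6 | 9.2 | 8.4 |

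The median split solves exp(−λc)S(c) = ½, giving c between 22.3 and 27.2 months. Putting the PFS limits into the same formulas, the 24-month gap runs from 5.4 to 16.4 months at 61.3% and from 11.5 to 45.3 months at 84.4%. Simulations of 1,000,000 patients per scenario agree with the table within simulation error.

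**Other OS shapes.** Exponential OS gives larger gaps, about 35 to 70 months. At medians 40 and 60 it implies 42 × (1 − 0.5^(24/m)) = 14.3 and 10.2 deaths before month 24, above the 8 reported by the end of J-Ph2. At 80 and 100 it implies 7.9 and 6.4, which that count does not exclude. The Weibull range is the more cautious one.

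**Samples of 42.** In 20,000 simulated studies per scenario, the longer-treated group had the higher median OS in 66% to 91%.

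**Dose reduction** (simulation; calibration B; m = 60 and 84; exponential time to first reduction, counted only if before stopping or death). With an assumed median time to reduction of 3 to 24 months, reduced patients gain about 2 to 15 months. With 1 to 2 months, the gain is under 2 months at k = 2 and about 5 to 8 months at k = 1.5.

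**Landmark at month 24.** Among patients alive at month 24, remaining survival is independent of stopping under the null, so the expected gap is zero (0.2 months or less in simulation). If stopping and death share prognosis (assumed gamma frailty, variance 0.25; k = 1.5 with m = 60, and k = 2 with m = 84), the landmark still shows about 12 to 13 months, against about 35 and 21 for the naive split.

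**The case against.** The analyses are descriptive, with no test, hazard ratio or effect claim, and Protocol 9.9 already warns about time-to-event interpretation and causality. That limits the harm. It does not remove a built-in artefact from curves that Protocol 12 intends for publication.

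The dose reduction group is undefined, so its bias is inferred and weaker: it shrinks if reductions come early, and confounding could change the observed direction. This stands. Only the immortal-time component has a known sign, though a reduction can occur only after first dose on any reading.

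The sizes rest on stopping being independent of death, which puts about 70% to 77% of early deaths on palbociclib under calibration A (1.6 of 2.3; 5.2 of 6.8). If early deaths mostly follow discontinuation, more of the gap would reflect a real link between duration and prognosis. This also stands: the figures illustrate and do not predict. The allocation of every death before month 24 to the short group holds regardless.

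A landmark loses patients from a set of at most 42 and leaves confounding. Both are true, so the landmark needs a caveat beside it. A caveat alone would leave the guaranteed survival time in the curves.

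**Conclusion.** The concern holds. Followed exactly, SAP 7.4 gives an OS comparison by palbociclib duration that is biased towards longer treatment whenever deaths occur before the cut. The same follows for dose reduction if the term means what it means in SAP 4.3.

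With no true effect and 1-year PFS at 75%, the false gap in median OS is 7.6 to 25.1 months at the 24-month cut and 8.4 to 26.6 months at the median split. It is zero at the 24-month cut if nobody died before then. These values assume Weibull OS, exponential stopping independent of death, and PFS as a proxy for time on treatment. The sponsor holds the death and dosing dates and can establish the number of early deaths directly.

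The primary OS estimate is untouched. This should be fixed before the subgroup results are reported, but it does not threaten the main result.

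**What to change.** In SAP 7.4, replace the OS subgroups by palbociclib duration with a 24-month landmark: include patients alive and in follow-up at month 24, group them by whether they are on or off palbociclib then, and count OS from month 24. Drop the median split or landmark it at that time point.

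Move the dose reduction group out of the SAP 4.4 baseline list and define it. Analyse it by a landmark at a time fixed in the SAP, or as a time-dependent covariate, using dose data from both databases as Protocol Table 1 provides.

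Report with the results: *The landmark removes the guaranteed survival time but not confounding by progression; differences are not an effect of treatment duration or dose.*

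The cost is SAP wording and a small amount of programming on data already held. The landmark stays within the planned Kaplan-Meier method; a time-dependent analysis would add a method the SAP does not now contain. Patients who die or are censored before the landmark leave that subgroup analysis, which lowers precision.

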7.5 Baseline Summary

Not applicable

7.6 Overall Study Status

The presence/absence of informed consent, the survival status, and the treatment status at the start/end of the study will be summarized along with the subject status at the end of the study. The study completion/discontinuation status and the reasons for study discontinuation among subjects who were receiving study treatment at the start of the study will be summarized.

Assessments of pre-existing and new lesions upon discontinuation of palbociclib and letrozole will be summarized along with data from J-Ph2.

The number of subjects with major protocol deviations will be listed.

The duration of survival follow-up will be estimated using a reverse Kaplan-Meier method.

7.7 Exposure to Study Treatment

Not applicable

7.8 Concomitant medications

Not applicable

7.9 Safety Endpoints

Not applicable

7.10 PK/PD Endpoints

Not applicable

8 REVISION HISTORY

See page 2.
